### Data Analysis:

Descriptive statistics will be used to describe the sample population, total satisfaction scores, and feasibility and fidelity of the protective device. Frequencies of nurse and caregiver reporting completion of the patient wearing the protective device will be calculated to evaluate feasibility and fidelity. Nurse satisfaction scores will be analyzed using a one sample t-test and descriptive statistics. Parent satisfaction scores will be analyzed using repeated measures ANOVA and descriptive statistics.

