**Form A**

IRB #

STU 2022-0306

**PROTOCOL FORM / RESEARCH  
DESCRIPTION**

If an item does not apply to your research project, indicate that the question is "**not applicable**" – do not leave sections blank

**Click once on the highlighted entry in each box to provide your response.** Click the item number/letter or word, if hyperlinked, for detailed instructions for that question. If your response requires inserting a table, picture, etc, you may need to first delete the box that surrounds the answer and then insert your table or other special document.

**1. Purpose and objectives.** *List the purpose and objectives:*

Title: Exploration of Central Venous Catheter Protective Devices in the Pediatric Population: A Mixed Methods Study

CVCs have multiple uses, including medication delivery (Government of Alberta., 2020) and provision of Total Parental Nutrition (TPN). While the CVC is necessary for the patient's treatment, it is not without risk. Patients with CVCs may experience catheter breaks, dislodgement, or central-line associated bloodstream infections (CLABSI). As a result, patients experience increased health care utilization, possible restriction of movement, and delayed development. The CDC established guidelines to prevent CLABSI in hospitalized pediatric patients that include keeping the catheter clean, dry, and intact (CDC, 2015). A paucity of literature supports nursing practice for preventing contamination, catheter dislodgement, and catheter breaks (Chamblee et al., 2020; Langford et al., 2021). One promising intervention is a wearable device (Gus Gear Vest) that can keep the catheter secure while protecting it from contamination and other risks.

Gap: There is a lack of research that focuses on wearable devices in pediatric patients.

The primary purpose of this study is to explore caregiver and nurse satisfaction of pediatric patients with CVCs that utilize a wearable protective device.

The specific aims of this study are to:

- 1) to determine the feasibility of utilizing a wearable device
- 2) to prospectively measure and evaluate parent and nurse satisfaction with the protective wearable device.

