#### a. Background

Previous studies have found that CVC complications and failure are recognized problems experienced by patients (Ullman et al., 2015b). One in four CVCs fail before completing intended therapy in the pediatric population (Ullman et al, 2015a). Mechanical complications may include catheter breaks and catheter dislodgement which may delay recovery or interrupt treatment (Cesaro et al., 2004). Mechanical complications are a common cause for repair, especially in the pediatric population, due to the child's lack of safety awareness, nearly constant movement, and poor impulse control (Cesaro et al., 2004). In 2020, 21,399 CLABSI's were reported by CDC (n.d.b). CVC complications lead to a significant burden on the patient and the healthcare system including additional time in the hospital, lost time receiving treatment, loss of access sites, and the potential for further complications including death (Peng et al., 2011; Ullman et al., 2015a). Additionally, there is a 3-fold increase in sepsis in the 30 days following line repair (Lungdren et al., 2012). There is a lack of research that focuses on preventing contamination of CVCs by bodily fluids, food/ liquids, and other contaminants outside of the traditional securement devices. CVC usage may impact the patient's quality of life (Tremolada et al., 2005). Parents of leukemia patients reported a higher quality of life when retaining prior activities or routines (Tremolada et al., 2005). However, there is a lack of research studies that focus on devices that promote normal levels of activities and routines in pediatric patients with CVCs while still maintaining the safety of the CVC.

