## Form A

IRB # STU 2022-0306

The PI and Co-PIs will provide training to the research team to promote consistency in data collection. Study team personnel will approach eligible patients for consent. Once consented, patients/ parents will be provided two protective wearable devices. Education on how to wear the protective wearable device will be provided. Demographic data will be captured utilizing chart review.

An interview with the parent on the device will be obtained at enrollment to the study. Interviews will be audio-recorded and transcribed verbatim using the TranscribeMe Application. Qualitative analysis will require thematic saturation which typically requires at least 8 interviews (Namey et al., 2016). Parents will be interviewed using the feasibility interview guide. Interviews will be open-ended questions lasting 15 to 45 minutes long utilizing an interview guide for consistency of interviewing probes may be utilized such as, "Can you tell me more about that?"

Parents will be requested to complete 30-day satisfaction survey every month for a total of three data collection period. Sampling will continue for up to 30 patients to meet minimum requirements for statistical analysis for feasibility and satisfaction data.

**Nurse data collection scheme:** If the patient is hospitalized, the nurse caring for the patient will be asked to complete the nurse satisfaction survey. Study participants hospitalized at time of enrollment in study or anytime during the study period.

**Setting:** The study will be conducted at a large, tertiary pediatric healthcare system on the primary Dallas campus. Primary targeted patients are within the inpatient and ambulatory settings for patient specialties: 1) gastroenterology, 2) transplant, and 3) pulmonary.

The gastroenterology floor has approximately 1124 admissions per year with about 40 TPN dependent patients that require external CVCs for treatment. Gastroenterology diagnosis that are seen include short gut syndrome, microcolon-intestinal hypoperistalsis syndrome. The gastroenterology population is also seen in the ambulatory setting with approximately 14,000 visits per year. Patients with central venous catheters admitted to inpatient oncology, transplant, pulmonary, general pediatrics, and rehabilitative floors will be considered as identified by the central line associated bloodstream infection committee or infectious disease to be approached by the study team.

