Every thirty days for 3 months parent satisfaction and feasibility of the protective wearable device will be collected using a quantitative survey. Patients may be approached within ambulatory clinic visits, inpatient visits, or by telephone. Study team will have a plus or minus seven-day timeframe around the 30-day window to collect the data. If the caregiver is present, then the caregiver will complete the survey on a Children's issued iPad via Microsoft Forms. If for some reason, the iPad is not working, which would be a rare occurrence, the caregiver will fill out a paper survey. Additionally, the electronic medical chart will be audited for any CVC complications such as line dislodgement, breaks, contamination, or CLABSI. At the end of the study data will be analyzed and collated.

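### The repeated measures ANOVA of three monthly parent surveys would normally drop any family that misses one; a mixed model on all surveys, with a 95% CI per month, is a cheap improvement

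*Combined protocol and SAP*

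**What the plan says.** Aim 2 in section 1 is "to prospectively measure and evaluate parent and nurse satisfaction with the protective wearable device". For parents, section 4.a sets the schedule: "Parents will be requested to complete 30-day satisfaction survey every month for a total of three data collection period". The sample is given as follows: "Sampling will continue for up to 30 patients to meet minimum requirements for statistical analysis for feasibility and satisfaction data". No significance level, power, standard deviation, correlation or expected loss accompanies that number.

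On collection, section 4.a states: "Study team will have a plus or minus seven-day timeframe around the 30-day window to collect the data". It also offers several routes of contact: "Patients may be approached within ambulatory clinic visits, inpatient visits, or by telephone".

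On analysis, the quantitative Data Analysis part says: "Parent satisfaction scores will be analyzed using repeated measures ANOVA and descriptive statistics". The same part covers level descriptively: "Descriptive statistics will be used to describe the sample population, total satisfaction scores, and feasibility and fidelity of the protective device". No section says what happens to a family with one or two surveys, and none mentions imputation, a mixed model or a confidence interval.

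**The concern.** A standard repeated measures ANOVA needs all three scores from a family. One missed survey removes that family's other two from the test, although they have already been collected. With at most 30 families there is little to spare, and this is the only inferential analysis planned for parent satisfaction.

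The ANOVA also tests only whether scores change over the months. That is a legitimate question, but Aim 2 asks first about satisfaction itself. The plan covers that descriptively without naming an interval.

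Some incomplete series are plausible. Section 2.a reports: "One in four CVCs fail before completing intended therapy in the pediatric population". Section 4.a also foresees that a patient may stop wearing the device during the study. The documents do not say whether surveys continue after either event. If families who leave differ in satisfaction from those who stay, an analysis of complete families can also be biased.

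**Working it through.** **Inputs from the documents.** Up to 30 families and 3 surveys each (section 4.a), so 30 × 3 = 90 possible surveys. The figure of 30 has no stated inputs behind it and cannot be reproduced.

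**Assumptions.** Within-family correlation ρ = 0.6, equal for all pairs of months, and SD = 1 unit. Detectable changes use a two-sided 5% level and 80% power. The missing rates are illustrative, because the documents give none.

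**1. Surveys missed independently with probability p**

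- Complete families = 30(1 − p)³.
- Surveys collected = 90(1 − p).
- Share of collected surveys discarded = 1 − (1 − p)².
- ANOVA standard error of the month 1 to 3 change = √[2(1 − ρ)/n] = √(0.8/n), with n complete families. At p = 0.2, n = 30 × 0.512 = 15.4 and √(0.8/15.36) = 0.228 SD.
- Mixed-model standard error: sum the expected information over the possible patterns of observed months, then invert.
- Detectable change: the linear month 1 to 3 change found with 80% power by the 2-df F test of month. ANOVA values use n rounded to 26, 22, 15 and 10.

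| p | Complete families | Discarded | SE, ANOVA | SE, mixed model | Ratio | Detectable change, ANOVA | Detectable change, mixed model |
|---|---|---|---|---|---|---|---|
| 5% | 25.7 | 10% | 0.176 | 0.169 | 1.04 | 0.56 SD | 0.54 SD |
| 10% | 21.9 | 19% | 0.191 | 0.176 | 1.09 | 0.61 SD | 0.56 SD |
| 20% | 15.4 | 36% | 0.228 | 0.191 | 1.20 | 0.76 SD | 0.61 SD |
| 30% | 10.3 | 51% | 0.279 | 0.210 | 1.33 | 0.96 SD | 0.68 SD |

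With 30 complete families the detectable change is 0.52 SD. At p = 20%, 90 × 0.8 = 72 surveys are collected and 3 × 15.4 ≈ 46 enter the ANOVA. The choice of ρ matters little: the ratios are 1.05, 1.10, 1.22, 1.37 at ρ = 0.3 and 1.04, 1.08, 1.18, 1.31 at ρ = 0.8.

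**2. Dropout: first survey complete, then a share h of remaining families lost before each later survey**

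Complete families = 30(1 − h)².

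| h | Complete families | Discarded | SE ratio | Detectable change, ANOVA | Detectable change, mixed model |
|---|---|---|---|---|---|
| 10% | 24.3 | 10% | 1.03 | 0.58 SD | 0.57 SD |
| 20% | 19.2 | 21% | 1.05 | 0.66 SD | 0.62 SD |
| 30% | 14.7 | 33% | 1.08 | 0.77 SD | 0.69 SD |

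If a quarter of families had stopped by month 3 (the section 2.a figure, used only as an illustration), (1 − h)² = 0.75 and h = 0.134. Then 22.5 families are complete, the standard error is about 3% larger, and the detectable change is 0.61 against 0.58 SD.

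**3. Does the mixed model behave at this size?** It was simulated with 30 families, a random intercept and denominator degrees of freedom equal to surveys − families − 2. Its type I error was 5.6, 4.7, 4.4 and 5.3% at p = 5, 10, 20 and 30%. Power at a true change of 0.615 SD was 89, 87, 79 and 71%, against 86, 79, 61 and 40% for the ANOVA.

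**4. Bias when dropout depends on satisfaction.** Simulated with 64% of families complete and a logistic dropout slope of up to 1 per SD. Sizes are in SD units.

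| Dropout depends on | Change: complete families | Change: mixed model | Month 3 mean: available surveys | Month 3 mean: mixed model |
|---|---|---|---|---|
| Previous, observed score | 0.07 | 0.00 | 0.20 | 0.00 |
| Current, unseen score | 0.07 | 0.13 | 0.27 | 0.13 |

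**5. Precision of level.** The 95% CI half-width for a monthly mean is t(0.975, n − 1)/√n. This is 0.37 SD with 30 families, 0.42 SD with 24 and 0.55 SD with 15, wide enough that the interval should be shown.

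**The case against.** The strongest case against is that the plan never says incomplete families are dropped. It names a method in one sentence and leaves the handling open. That is correct: what the text shows is the absence of a rule, and the loss follows only from the usual form of the test.

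Second, the gain is small where gaps seem most likely. Under dropout the standard error grows by 3 to 8%, and clinic, inpatient or telephone contact within seven days either side works against scattered misses. The catheter failure figure has no time frame and is not tied to missed surveys. All of this stands and limits the size of the point.

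Third, the descriptive statistics can use every survey and would probably include an SD, from which an interval follows. This also stands. It means the discarded data concern the test of change, and the interval could be added without changing the model.

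Fourth, the mixed model is not always better. If families leave because of a current score that nobody sees, it roughly doubles the bias in the change. That is a reason to state the assumption and keep the complete-family result, not a reason to discard collected surveys by default.

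Finally, the study is exploratory with no stated power target, so detectable changes serve here only as a yardstick.

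**Conclusion.** The point holds as a cheap improvement, not as an error that undermines the study. No section gives a rule for a missed survey or names another model, and the standard ANOVA would leave collected data unused. For the month 1 to 3 change the loss is trivial at 5% missed and small under dropout. It becomes material at about 20% or more scattered misses, where the standard error is 20% larger or worse. These sizes rest on assumed missing rates and equal correlation between months; varying that correlation from 0.3 to 0.8 does not alter the conclusion. With complete data the two analyses give essentially the same test of month. The mixed model's advantage in bias depends on missingness being explained by observed scores.

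**What to change.** In the quantitative Data Analysis part of section 4.a:

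- Replace the ANOVA with a linear mixed model: month as a factor, a random intercept per family, all available surveys, and Kenward-Roger or Satterthwaite degrees of freedom.
- Report the estimated mean at each month with a 95% CI alongside the test of change.
- Report the number of missed surveys at each month, with reasons.
- State that the model assumes missingness depends only on observed scores, and show the complete-family ANOVA as a sensitivity check for the change.

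Also confirm that parent surveys carry the study code. The statement on anonymous survey records sits in a bullet about nursing data, but if it covered parents, neither method could link a family's three surveys.

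The cost is about two sentences and one missing-data line per month, in standard software, with no extra patients or visits. The downsides are slightly more analysis work and the missing-at-random assumption.

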### Protected Health Information (PHI):

- Patient names will be collected to assign a unique identifier code by the study team

## Form A

IRB #	STU 2022-0306
-------	---------------

- The PHI/Codes will be stored behind Children's firewall in a password protected, limited access file to only study team personnel for the entire project.
- Consent forms will be collected and locked in a file in a research cabinet in a locked office.
- Once the study is completed and data analyzed the PHI/codes will be destroyed upon study publication acceptance.
- Nursing data gathered will be on an anonymous basis and will not have any of the 18 HIPPA privacy rule identifiers cited by the U.S. Department of Health and Human Services. All survey records will be recorded anonymously in Microsoft excel used within the Children's firewall.

**Form A**

IRB #	STU 2022-0306
-------	---------------

**4.b. List of the study intervention(s) being tested or evaluated under this protocol**

	N/A - this study does not test or evaluate an intervention. Skip to item 4.d.		
#	Study intervention(s) being tested or evaluated under the protocol  Add or delete rows as needed	Affiliate Place a check next to institution(s) where the intervention will be performed	Local Standard Practice? Indicate whether the intervention is considered acceptable practice locally for applicable institutions
	N/A	 UTSW  Yes  PHHS  Yes CMC      Yes  THR  Yes  TSRH  Yes  Other: _____  Yes   TSRH  Yes  Other: _____  Yes	

**4.c. Risk:Benefit Analysis of study interventions being tested or evaluated under this protocol**

For each study intervention identified in section 6b above, complete a risk:benefit analysis table.

*(Two tables are provided, copy & paste additional tables as needed or delete both tables if this study does not test an intervention)*

**Form A**

IRB #	STU 2022-0306
-------	---------------

4.c. N/A	
List each group exposed to this intervention on a separate line. (e.g., experimental, control, Arm A, Arm B, etc) Or state All Groups/Subjects	For each group, list the benefits of this intervention. (Benefits can be directly from the intervention or from a monitoring procedure likely to contribute to the subject's well being). If there are no benefits, state "none".

**If you are requesting a Waiver of Informed Consent, complete the table below.**

If you have a consent form, **list the reasonably foreseeable risks** in the consent form (and do not complete this section).

List the risks according to the probability (likely, less likely or rare) and magnitude (serious or not serious). (include: 1) expected adverse events; 2) rare and serious adverse events; 3) all other psychological, social, legal harms) Do not delete frequency. Frequency must be estimated because it will assist you with determining which adverse events will require prompt reporting.

	Not serious	Serious
Likely These risks are expected to occur in more than 20 out of 100 subjects.	•	•
Less likely These risks are expected to occur in 5- 20 subjects or less out of 100 subjects.	•	•
Rare These risks are expected to occur in less than 5 subjects out of 100		•

	
4.d. List ALL other research procedures or components not listed in table 4.b.
 
The combination of Tables 4b and 4d should account for all of the research procedures that will take place during this study.
 
Consider grouping similar procedures under a single component (e.g., blood work, CT = safety assessments)

--	--

#	
Research component
 
 
individual procedures
 
 
example:
 
Eligibility Assessments
 
 
History and physical
 
Questionnaire
 
Laboratory tests
 
	
Column A
 
Local Standard Practice Indicate the number of times each procedure will be performed as stipulated in the research plan that would be performed if the participant were not participating in the
	
Column B
 
Research Only
 
Indicate the number of times each procedure will be performed solely for research purposes (meaning that the participant would not undergo the same number of procedures or would not undergo the procedure(s) at the same frequency if
	
Column D
 
Risks
 
If you are requesting a Waiver of Informed Consent, complete the table below.
 
List the reasonably expected risks for each procedure or group of procedures under the following categories as appropriate:
 
 
• Serious and likely;
 
• Serious and less likely;
 
• Serious and rare;
 
• Not serious and likely;
 

---	--	---	--	---

**Form A**

IRB #	STU 2022-0306
--------------	----------------------

Add or delete rows as needed	study.	they were not participating in the study)	
 
• Not serious and less likely
 

1			
2			
3			
4			
5			
4			

**5. Safety Precautions. (Describe safeguards to address the serious risks listed above.)**

**a.** Describe the procedures for protecting against or minimizing any potential risks for each of the more than minimal risk research procedures listed above.

The risks are not "More than minimal risk"

**b.** Where appropriate, discuss provisions for ensuring necessary medical or professional intervention in the event of adverse events, or unanticipated problems involving subjects.

The risks are not "More than minimal risk"

**c.** Will the safeguards be different between/among groups?

Yes

No

The risks are not "More than minimal risk"
